6.4.7 Safety Monitoring

Vital signs will be assessed immediately before and after injection of [⁶⁸Ga] PSMA-11 (HR and supine BP). Patients will be monitored for adverse events during injection and after completion of the imaging study. Additionally, patient's vitals (HR and supine BP) will be checked at the completion of the imaging study prior to leaving the imaging center.

6.4.8 Patient Follow-Up

Patients will be called within 24 hours of [⁶⁸Ga]PSMA-11 administration to ensure no adverse events have occurred. Patients will be seen in the clinic if there are any concerning study related adverse events requiring further evaluation.

6.5 Radiation Treatment Planning and Delivery

6.5.1 RADIOTHERAPY SIMULATION

CT simulation for radiotherapy planning will be performed within 8 weeks of the initiation of neoadjuvant androgen suppression (per standard-of-care clinical guidelines) and within 10 weeks of the PSMA staging scan. Patients will be asked to have an empty rectum and full bladder at time of simulation. Bowel regimen will consist of two 17g doses of polyethylene glycol laxative and two 125mg doses of simethicone the day prior to simulation. Patients will be asked to drink 24 ounces of water 30 minutes prior to simulation in order to ensure bladder fullness. A custom molded foam form will be created to aid patient immobilization. A retrograde urethrogram will be performed to improve visualization of the prostate apex ⁶. The CT scan will extend from the L1/L2 to mid-femur and will utilize \leq 3mm slice thickness. Intravenous iohexol contrast will be utilized to improve visualization of lymph nodes. All CT simulation parameters and patient preparation is per standard-of-care clinical guidelines.

6.5.2 RADIOTHERAPY TARGET VOLUME DELINEATION (Figure 1)

Varian Eclipse software (Varian Medical Systems LLC, Palo Alto, CA, USA) will be used for radiotherapy target delineation and treatment planning. For all patients we will initially define traditional standard-of-care clinical target volumes for the treatment of high risk prostate cancer:

CTV_{P+SV} will contain the entire prostate gland and portion of the seminal vesicles at risk for tumor involvement. At least the proximal 1cm of the seminal vesicles. In cases where gross seminal vesicle invasion is identified the entire seminal vesicles will be included.

CTV_{eLN} will contain the elective lymph node target volumes. Elective nodal regions will be delineated in accordance with published consensus guidelines⁷ and will include the obturator, internal iliac, external iliac, and distal common iliac chains.

Next, the PSMA PET scan will be rigidly co-registered to radiation simulation CT scan. Rigid co-registration is preferred for two specific reasons: (1) we recognize that 8-10 weeks of androgen suppression between PSMA-PET/MRI and radiotherapy simulation may lead to changes in LN size that may lead to error in deformable registration, and (2) prior experience with PSMA-PET/MRI co-

[figure not shown]

Figure 1: Example of fluciclovine-PET/MRI directed radiotherapy treatment planning. Left image shows the $[^{18}\text{F}]$ fluciclovine PET-MRI with lower window of PET window set to 1.3 times blood pool. The suspicious LN is segmented in red. Right image is the treatment planning CT for the same patient with $\text{CTV}_{\text{LN BOOST}}$ delineated in green and the associated PTV in blue.

registration in the biochemical recurrence setting indicates that rigid co-registration results in good anatomic agreement in the majority of cases⁸. Using the registered PSMA-PET/MRI we will delineate an additional CTV:

$\text{CTV}_{\text{LN BOOST}}$ will contain LNs with maximum SUV greater than 1.3 times the blood pool reference. The LNs will be segmented on the MRI portion of the PSMA-PET/MRI and superimposed on the co-registered CT simulation scan. The resulting structure will be edited to create $\text{CTV}_{\text{LN BOOST}}$ by excluding bowel structures and barriers to tumor spread (e.g. muscle or bone). We note that suspicious LNs are likely to be smaller on the CT simulation scan due to the initiation of androgen suppression, but $\text{CTV}_{\text{LN BOOST}}$ will not be further reduced so as to account for potential microscopic tumor extension. This concept is analogous to involved node radiotherapy utilized for post-chemotherapy consolidation of lymphoma⁹.

Planning target volume (PTV) expansions for $\text{CTV}_{\text{P+SV}}$ will be 4mm posteriorly and 7mm in all other directions. PTV expansions for CTV_{eLN} and $\text{CTV}_{\text{LN BOOST}}$ will be 8mm in all directions.

6.5.3 RADIOTHERAPY TREATMENT PLANNING AND DELIVERY

We will utilize a moderately hypofractionated dose regimen which is standard-of-care at our institution. Our institutional technique for elective pelvic irradiation with a simultaneous integrated boost to the prostate and proximal seminal vesicles has been described in multiple peer-reviewed publications¹⁰⁻¹³ and moderate hypofractionation is recognized by the National Comprehensive Cancer Network as an appropriate dose regimen for men with high-risk and node positive prostate cancer¹⁴. We will prescribe 70 Gy to $\text{PTV}_{\text{P+SV}}$, 60.2 Gy to $\text{PTV}_{\text{LN BOOST}}$, and 50.4 Gy to PTV_{eLN} .

simultaneously in 28 fractions of 2.5 Gy, 2.15 Gy, and 1.8 Gy, respectively. Treatment plans will be generated to meet the criteria specified in **Table 2**. The prescription to $PTV_{LN\ BOOST}$ may be escalated beyond 60.2 Gy at the discretion of the treating radiation oncologist if all organ-at-risk constraints are met, but will not be allowed to exceed 70 Gy. Treatment plans will utilize either intensity modulated radiotherapy (IMRT) or volumetric modulated arc therapy (VMAT). Daily image guidance will be performed utilizing cone beam CT performed prior to the delivery of each fraction and emphasis of patient alignment will be at the prostate-rectum interface.

Table 2: Pre-specified dosimetric criteria for plan acceptability.			
Structure	Dosimetric Parameter	Per Protocol	Variation Acceptable
PTV_{P+SV}	V70 Gy[%]	≥95%	≥90%
	Maximum dose	<75 Gy	<77 Gy
$PTV_{LN\ BOOST}$	V60.2 Gy[%]	≥90%	- ¹
	Maximum dose	<66 Gy	<68 Gy
PTV_{eLN}	V50.4 Gy[%]	≥95%	≥90%
	Maximum dose	<55 Gy	<58 Gy
Rectum	V70 Gy[cc]	<3cc	<5cc
	V60 Gy[%]	<10%	<15%
	V50 Gy[%]	<25%	<40%
Small bowel	Maximum dose	<54 Gy	<58 Gy
	V54 Gy[cc]	0cc	<20cc
	V45 Gy[cc]	<120cc	Not specified
Bladder	V60 Gy[%]	<20%	<25%
	V40 Gy[%]	<50%	<60%
Femoral heads	V50 Gy[%]	<5%	<10%

¹No minimum acceptable coverage of $PTV_{LN\ BOOST}$ is specified due to potential overlap between the target volume and bowel structures is may occur. In such instances effort should be made to ensure $CTV_{LN\ BOOST}\ V60.2\ Gy[%] \geq 90\%$.

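### The nodal boost text and Table 2 set incompatible dose limits in two places, and the Aim 2 endpoint of boost feasibility is tied to no stated criterion

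*Combined protocol and SAP*

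**What the plan says.** Section 6.5.3 prescribes 70 Gy to PTV_P+SV, 60.2 Gy to PTV_LN BOOST and 50.4 Gy to PTV_eLN in the same 28 fractions. "Treatment plans will be generated to meet the criteria specified in" Table 2, whose title is "Pre-specified dosimetric criteria for plan acceptability". The next sentence says the boost prescription "may be escalated beyond 60.2 Gy at the discretion of the treating radiation oncologist". To this it attaches one condition and one upper limit, namely "if all organ-at-risk constraints are met, but will not be allowed to exceed 70 Gy".

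Table 2 limits the maximum dose in PTV_LN BOOST to <66 Gy per protocol and <68 Gy as an acceptable variation. For PTV_eLN the limits are <55 Gy and <58 Gy. Boost coverage (V60.2 Gy) must be at least 90% per protocol, but the variation cell is blank. Footnote 1 explains the blank by possible overlap with bowel and adds: "In such instances effort should be made to ensure" 90% coverage of the boost CTV at 60.2 Gy.

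Under Section 6.5.2 the elective CTV "will include the obturator, internal iliac, external iliac, and distal common iliac chains". The PTV expansion for both nodal CTVs "will be 8mm in all directions". On the seminal vesicles, the same section says: "In cases where gross seminal vesicle invasion is identified the entire seminal vesicles will be included".

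Section 6.5.5 makes the Aim 2 primary endpoint the number of scan-positive patients in whom the boost is feasible, with at least 90% expected. Scan-positive includes suspected seminal vesicle invasion without nodal disease. The Aim 2 primary analysis in Section 6.6.3 is a Bland-Altman comparison of imaging parameters plus unspecified descriptive analysis. It names no feasibility count and no rule for one.

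**The concern.** Two dose rules cannot both be followed as written. For an escalated boost, the text gives one ceiling and the table another, and neither is said to take precedence. For an ordinary unescalated boost to a node in the elective chains, delivering the prescription breaks the elective-volume maximum if that row is read literally.

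This matters statistically because Aim 2 counts feasible boosts, and Table 2 is the only pre-specified set of plan criteria in the protocol. If its rows conflict, and if no section says that meeting them is what feasible means, someone must settle the reading later, possibly with the plans in view. At most 10 patients can contribute, so a few such decisions could determine the reported proportion.

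**Working it through.** **Prescriptions (Section 6.5.3).** 28 × 2.5 = 70.0 Gy, 28 × 2.15 = 60.2 Gy and 28 × 1.8 = 50.4 Gy. All three stated totals reproduce.

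**Table 2 maxima against each volume's own prescription**

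| Volume | Prescription (Gy) | Per protocol maximum | Variation maximum |
|---|---|---|---|
| PTV_P+SV | 70.0 | 75/70 = 107.1% | 77/70 = 110.0% |
| PTV_LN BOOST | 60.2 | 66/60.2 = 109.6% | 68/60.2 = 113.0% |
| PTV_eLN | 50.4 | 55/50.4 = 109.1% | 58/50.4 = 115.1% |

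Each row appears to be set relative to its own volume's base prescription.

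**Conflict 1: escalated boost.** Some part of a volume must receive the prescribed dose, so the maximum is at least the prescription.

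- At 66 Gy or more, the <66 Gy limit cannot be met.
- At 68 to 70 Gy, neither limit can be met.
- At 70 Gy the excess is at least 70 − 66 = 4 Gy and 70 − 68 = 2 Gy.

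Below those values, compliance depends on homogeneity. Headroom above the prescription is 9.6%/13.0% at 60.2 Gy. It falls to 66/64 − 1 = 3.1% and 68/64 − 1 = 6.3% at 64 Gy, and to 0% and 68/66 − 1 = 3.0% at 66 Gy. The documents do not say what homogeneity is achievable, so I do not estimate how much of the escalation range fits.

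**Conflict 2: base boost inside the elective volume.**

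1. If CTV_LN BOOST lies within CTV_eLN, adding 8 mm to both keeps PTV_LN BOOST within PTV_eLN.
2. Where 60.2 Gy is delivered there, the elective maximum is exceeded by at least 60.2 − 55 = 5.2 Gy (per protocol) and 60.2 − 58 = 2.2 Gy (variation).
3. Complete nesting is not needed. With boost V60.2 Gy of at least 90%, at most 10% of PTV_LN BOOST is below 60.2 Gy. If more than 10% of it overlaps PTV_eLN, some of PTV_eLN must receive at least 60.2 Gy.

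No escalation is involved. Of the 11 nodal stations in Section 6.4.6.3, six (obturator, internal and external iliac on each side) belong to the elective chains. Two (common iliac) do so in their distal part. The two inguinal stations and the retroperitoneal one are not among the listed chains.

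**Endpoint.** Neither Section 6.2 nor Section 6.5.5 defines feasible or cites Table 2. At variation level there is no minimum boost coverage, and the 90% CTV target in footnote 1 is an aim for bowel-overlap cases only. With n positive patients (n is not given, so take 1 to 10), reaching 90% requires n out of n for every n from 1 to 9; for example, 8/9 = 88.9% falls short. For n = 10 it requires 9. Below 10 positive patients, one reclassified plan can decide whether the expectation is met.

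**The case against.** **The specific sentence governs escalation.** It follows the general instruction, states its own condition and ceiling, and the boost coverage row is keyed to 60.2 Gy. One can read the boost rows as describing the base prescription only. That reading is reasonable, but nothing in the protocol states it. What stands is that escalation is optional, that the strict clash starts only at 66 Gy (per protocol) or 68 Gy (both columns), and that nothing says any patient will be taken that high.

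**No planner would apply the elective maximum inside a boost volume.** Probably true. The ratios in the table above suggest that each maximum was meant for tissue treated at that dose level. This makes the second conflict a missing note, but as written the row still fails a plan that delivers the prescription.

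**The table already shows the threshold.** Its title concerns acceptability and its second column is for acceptable variations, so variation level is the evident pass mark. I accept that. What is missing is the link from feasible to the table, and a minimum for boost coverage.

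**Stronger readings to avoid.** A reader might infer from the blank cell that a plan with no boost would count as a feasible boost. The documents do not support this: Section 6.5.3 prescribes 60.2 Gy to the boost volume, and Section 6.5.5 says positive patients are planned with a boost. A reader might also infer a safety failure, but escalation remains conditional on every organ-at-risk limit. Nor does a go/no-go decision turn on the 90% figure, because the protocol sets no such rule.

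**Conclusion.** The concern holds in a limited form. Section 6.5.3 and Table 2 conflict for boost prescriptions of 66 Gy or more (per protocol) and of 68 to 70 Gy (both columns), by at least 4 and 2 Gy at the 70 Gy limit. Read literally, the PTV_eLN maximum is also exceeded by at least 5.2 and 2.2 Gy when an elective-chain node receives the base boost. The first conclusion assumes only that the prescribed dose is reached somewhere in the volume. The second assumes that the row applies to the whole of PTV_eLN, which is what the text says but probably not what was meant. The documents do not show how many patients either would affect.

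The consequence is inconsistent planning and an Aim 2 count whose meaning is not fixed in advance. Intact organ-at-risk limits, the pilot design and the absence of a decision rule keep the severity modest. It is still worth correcting, because feasibility is the main result Aim 2 would hand to a larger trial.

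**What to change.** Before any plan is scored:

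1. **One ceiling for an escalated boost.** By default, make escalation subject to the PTV_LN BOOST maximum-dose row. The alternative is for the radiation oncology investigators to restate that row relative to the escalated prescription. That is a clinical decision: keeping the present ratios at 70 Gy would give 70 × 66/60.2 = 76.7 Gy and 70 × 68/60.2 = 79.1 Gy, above the 75 and 77 Gy allowed in the prostate volume.
2. **Elective maximum.** Evaluate it on PTV_eLN minus the higher-dose PTVs, with a fall-off margin set by the same investigators.
3. **Definition of feasible.** Require Table 2 at least at variation level and CTV_LN BOOST V60.2 Gy of at least 90%. Report bowel-overlap plans that miss the coverage target separately. Add the resulting count and its denominator to Section 6.6.3.
4. **Seminal-vesicle-only positives.** Report them separately. They have no nodal boost, and when invasion is gross the vesicles are already in the 70 Gy volume.

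The cost is a short amendment: a table note, a changed sentence and an endpoint definition, with no added patients or procedures. The drawback is that item 3 turns the footnote's aim into a requirement, so a few bowel-overlap plans may be classed as not feasible. Separate reporting keeps that visible.

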6.5.4 RADIOTHERAPY ASSESSMENTS

Clinical toxicity during and after radiation therapy will be scored using the Common Terminology Criteria for Adverse Events version 5.0 (CTCAE v5.0). Response to therapy will be assessed with interval PSA measurement. All of these measures will be assessed per standard-of-care intervals for all patients undergoing radiation therapy for prostate cancer. We will utilize a battery of validated measures:

Table 3: Study Calendar.

	Pre-Study	Imaging Visit - 1-2 weeks before radio-therapy	As part of clinical care
H&P	X		X
PSMA-11 PET-MRI		X	
PSA†			X
CTCAE Toxicity Assessment†			X

†Performed as part of clinical care

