This clinical feasibility study will investigate the use of PSMA-PET/MRI to guide radiation treatment planning and delivery in patients with known or suspected locally metastatic prostate cancer at the time of diagnosis. The patients will undergo a single PSMA-PET/MRI (or PET/CT in some circumstances) prior to initiation of treatment. Following development of a PSMA-PET guided radiation treatment plan, therapeutic radiation will be delivered per standard-of-care parameters and assessments of feasibility and tolerability will be performed. A total of 10 patients will be enrolled in this study. If the PET/MRI demonstrates a suspicious finding that may make a patient ineligible for radiation therapy, the treating clinician (including urology and radiation oncology) will be alerted, and the decision to pursue biopsy and/or alter the patient's treatment plan will be based on standard of care imaging and consensus after presenting the case at the GU tumor board.

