6.3 Investigational Plan

6.3.1 Study Design

- Prospective IRB-approved study enrolling 10 patients with locally metastatic prostate cancer for pretreatment PSMA-PET/MRI prior to the initiation of treatment
- All patients will undergo standard-of-care clinical evaluation and imaging workup with nuclear medicine bone scan and either CT of the abdomen and pelvis or MRI pelvis
- Patients will undergo standard-of-care androgen deprivation therapy following PSMA-PET/MRI and prior to radiation therapy
- If study PET/MRI demonstrates a suspicious finding that may preclude a patient radiation therapy, the treatment team will be alerted to potentially investigate the finding further (i.e. additional imaging or biopsy)
- Acute radiation toxicities will be assessed at standard-of-care intervals

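### Table 3 places the only PSMA PET/MRI 1 to 2 weeks before radiotherapy; if the 8-to-10-week interval in section 6.5.2 holds, that is at least 6 weeks too late

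*Combined protocol and SAP*

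**What the plan says.** Five places in the combined protocol and SAP bear on when the scan takes place.

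- **Section 6.5.4, Table 3 (study calendar).** The PSMA-11 PET-MRI is marked in one column only, headed "Imaging Visit - 1-2 weeks before radio-therapy".
- **Section 6.0.** Patients will "undergo a single PSMA-PET/MRI (or PET/CT in some circumstances) prior to initiation of treatment". There is one scan, so every timing statement refers to the same event.
- **Section 6.3.1.** The design is "pretreatment PSMA-PET/MRI prior to the initiation of treatment". It adds: "Patients will undergo standard-of-care androgen deprivation therapy following PSMA-PET/MRI and prior to radiation therapy". This fixes the order (scan, androgen deprivation, radiotherapy) but gives no durations.
- **Section 6.5.1.** CT simulation takes place "within 8 weeks of the initiation of neoadjuvant androgen suppression" and "within 10 weeks of the PSMA staging scan". Both are upper limits.
- **Section 6.5.2.** In explaining the choice of rigid co-registration, the plan recognises "8-10 weeks of androgen suppression between PSMA-PET/MRI and radiotherapy simulation". On the boost volume it says: "The LNs will be segmented on the MRI portion of the PSMA-PET/MRI and superimposed on the co-registered CT simulation scan". It expects suspicious nodes to be smaller by simulation because of suppression, and it deliberately does not trim the boost volume to match.

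Nothing in the document reconciles the Table 3 heading with the interval in 6.5.2.

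**The concern.** A study calendar is what staff use to book visits, and this one gives the week for the trial's single investigational procedure. The heading does not fit the narrative sequence once the interval in 6.5.2 is taken into account.

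The harm is conditional. It arises only if the calendar is followed while the suppression course of 6.5.2 is kept. The scan would then be taken on androgen suppression, although sections 6.0 and 6.3.1 call for it before treatment.

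The consequence that can be traced in the documents concerns the boost contour. Section 6.5.2 relies on the scan showing nodes as they were before suppression, and it keeps that volume even if the nodes later shrink. An MRI acquired after suppression had started could show nodes that were already smaller, which works against that intent. With 10 patients and no replacement (section 6.3.6), each mistimed scan would affect one tenth of the enrolled sample.

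**Working it through.** No sample-size formula is involved; this is interval arithmetic.

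**Inputs**

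| Quantity | Value (weeks) | Source |
|---|---|---|
| Scan to radiotherapy, calendar | 1 to 2 | Table 3 |
| Scan to simulation, expected | 8 to 10 | 6.5.2 |
| Start of suppression to simulation, *a* | at most 8 | 6.5.1 |
| Scan to simulation, limit | at most 10 | 6.5.1 |
| Simulation to radiotherapy, *d* | not given; *d* ≥ 0 | by necessity |

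**Step 1. Discrepancy if the 6.5.2 interval holds.** Scan to radiotherapy equals scan to simulation plus *d*.

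- Minimum under 6.5.2: 8 + *d* ≥ 8 weeks.
- Maximum under Table 3: 2 weeks.
- Smallest discrepancy: 8 − 2 = 6 weeks, for any *d*.
- Largest discrepancy with *d* = 0: 10 − 1 = 9 weeks.
- Any planning time widens the gap. With an assumed *d* of 2 weeks, scan to radiotherapy is 10 to 12 weeks and the discrepancy is 10 − 2 = 8 to 12 − 1 = 11 weeks.

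**Step 2. Does the conflict survive without 6.5.2?** Suppression starts *a* + *d* weeks before radiotherapy. A scan 2 weeks before radiotherapy precedes suppression only if *a* + *d* ≤ 2; a scan 1 week before requires *a* + *d* ≤ 1. Section 6.5.1 says only that *a* ≤ 8, so these short values are not excluded. On sections 6.3.1 and 6.5.1 alone the heading could hold, with suppression starting no more than 2 weeks before radiotherapy. The 6-week figure therefore depends on 6.5.2.

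**Step 3. Does the reading of 6.5.2 matter?** Taken literally, 8 to 10 weeks is the time on suppression, which meets the 8-week cap in 6.5.1 only at exactly 8 weeks. It can also be read as the whole interval from scan to simulation, which fits the 10-week limit better. The 6-week minimum is the same on both readings, because each puts the scan at least 8 weeks before simulation. How far into suppression a calendar-timed scan would fall does depend on the reading, and on the unstated *d*, so no figure is given for it.

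**The case against.** The strongest reply is that 6.5.2 schedules nothing. The 8 to 10 weeks appears in a clause explaining why rigid registration is preferred, while the operative limits in 6.5.1 set no minimum. That stands, and it is why the 6 weeks is stated as conditional. It does not remove the conflict: the clause is the plan's only statement of the expected interval, and the same section relies on suppression having shrunk nodes by simulation.

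A second reply is that staff would follow the design. Sections 6.3.3 and 6.3.4 require treatment-naïve patients and exclude anyone on current or past prostate cancer treatment, and 6.3.1 sets out the order. This also stands in large part. Eligibility is judged at enrolment and does not by itself date the scan, but the narrative order is clear and the calendar heading is the outlier. This supports a minor rating.

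A third is that the heading was meant to say 1 to 2 weeks before androgen deprivation. The difference between the 6.5.1 limits, 10 − 8 = 2 weeks, is compatible with that, but it is inference. If it was the intent, the heading still needs correcting.

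On harm, the mitigations are real. The boost margin is 8 mm. The obturator, internal iliac, external iliac and distal common iliac chains receive 50.4 Gy electively, so in those chains a smaller boost contour would generally forgo the boost increment (60.2 − 50.4 = 9.8 Gy at the base prescription) rather than all dose.

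A reader might go further and infer that different nodes would be boosted, or that Aim 1 would be biased in a known direction. The documents support neither. Nodes are selected by SUV, and nothing is said about how suppression changes PSMA uptake. MRI scores do depend on node size and morphology (6.4.6.3), but MRI and fused PET/MRI are read from the same session, so timing would touch both sides of that comparison.

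**Conclusion.** Wrong as written; severity minor. The Table 3 heading conflicts with the order in 6.3.1 taken together with the interval in 6.5.2. If that interval holds, the heading is at least 6 weeks out, assuming only that simulation does not follow the start of radiotherapy. Section 6.5.1 alone would not establish any minimum.

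Confidence is high for the mismatch in wording. It is not high for the harm, which needs staff to follow the calendar over the stated design and has no size that the documents can supply. It would be too strong to conclude that patients will be scanned on suppression, since the narrative says the opposite. The point changes no sample size or error rate; section 6.6.1 makes no formal power calculation.

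**What to change.** Change the Table 3 column heading to *Imaging visit - before start of androgen suppression and within 10 weeks before CT simulation*. Both parts come from the plan itself (sections 6.3.1 and 6.5.1), and this change alone resolves the error.

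Optionally, as a separate tidy-up, reword the 8-to-10-week phrase in 6.5.2 to agree with the 6.5.1 limits, for example *up to 8 weeks of suppression, and up to 10 weeks in all, from scan to simulation*.

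The cost is one heading, and at most one phrase, in an amendment. No procedure, visit or data item is added.
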